#### 7.6.5. Visit Re-labeling

In case of early termination of study, the Month 6/EOT and Month 7/EOS visit will be re-labeled chronologically and stored in variable AVISIT in all visit-based ADaM data sets.

Based on the visit date and the randomization date, AVISIT will be calculated as

$$\text{Re-labeled visit} = (\text{Visit Date} - \text{Randomization Date}) / 28^*$$

\* rounded to the nearest month

Assessment dates will be compared to the visit date reported on the eCRF form 'Visit'. If the assessment date is equal to a visit date that belongs to visit which is different from the originally reported visit, then the visit is remapped to the visit reported on the 'Visit' form.

## 8. STUDY POPULATION SUMMARIES

The ITT analysis set will be used for all study population summaries unless otherwise stated. Summaries for other analyses sets will be provided only if the number of subjects substantially (>10%) differs from the ITT counts. Summaries of the baseline data for assessments also collected after randomization will be presented together with post-randomization data, as appropriate.

### 8.1. Subjects Disposition

For subjects screened, the number of subjects who are screened, the number of subjects who failed screening, and the reasons for screen failure will be summarized.

Subject disposition will be summarized to present the number of subjects who are randomized, the number and percent of subjects who are randomized and treated, the number and percent of subjects who completed/discontinued from the study or study drug(s) and the reason for discontinuation (including COVID-19). Percentages will be based on the ITT analysis set.

### 8.2. Demographic and Baseline Characteristics

Demographic and baseline characteristic variables will be summarized. These variables include country, age, sex, ethnicity, race, height, weight, BMI, FEV1, the stratification variables region (North America, Europe, and Rest of World) and history of MAC lung infection (initial or subsequent), and PROMIS F-SF 7a T-scores.

$$\text{BMI (kg/m}^2\text{)} = \text{weight (kg) (baseline value)} / [\text{height (cm)/100}]^2$$

In addition, patient count with MAC infection at baseline (*Mycobacterium avium* complex overall, *M. avium*, *M. intracellulare*), and other speciated and unspeciated MAC) will be provided.

### 8.3. Protocol Deviations

Deviations from the study protocol will be monitored throughout the conduct of the study. Rules and definitions are included within the study document INS-415/INS-416 Protocol Deviation Management Plan.

Major protocol deviations that affect primary efficacy and safety assessments (as applicable), the safety of a subject or the scientific value of the study will be summarized descriptively.

The PD subtypes will be combined into the following categories:

- GCP: I01, I02, I03, I06, I07, I16
- Safety and Oversight: I05, I11, I12, I13
- Documentation: I08, I09, I10,
- Regulatory compliance: I04, I14
- I/E criteria: P02, P03
- Investigational product/concomitant medications: I15, P04, P05, P06, P09

- Endpoint assessment: P07
- Study procedures: P08, P10
- Other: P13

#### **8.4. Medical History**

All medical history will be coded using MedDRA. The incidence of medical history will be summarized using descriptive statistics by SOC and PT. Subjects are counted only once in each SOC and only once in each PT.

#### **8.5. COVID-19 Impact**

Potential COVID-19 impact is captured in the eCRF and will be summarized by subject.

Subject disposition summary and listing will include:

- Screen failure related to COVID-19
- Treatment discontinuation related to COVID-19
- Early termination of study related to COVID-19

AE overview table and listings will include:

- AEs that fall into the category of COVID-19 related

Summary table and listing of dose interruption will include:

- Dose interruption related to COVID-19

Summary and listing of protocol deviations will include:

- Protocol deviations due to COVID-19

## **9. EFFICACY**

### **9.1. General**

#### **9.1.1. Reporting Statistics**

Nominal p-values will be provided for all efficacy analyses in which differences between groups and 95% CIs are evaluated.

#### **9.1.2. Usage of the covariates in the statistical models**

The study was randomized with two stratification strata: history of MAC disease and region (North America, Europe, and Rest of World). The statistical modeling using these categorical variables would imply a total of 12 strata combinations: 2 (treatments) \* 2 (history of MAC disease) \* 3 (geographical regions). Since the sample size for this study is 100 subjects, it is expected for some strata to have empty cells, resulting in inestimable parameters. Therefore, geographical region is not used in the model for all analyses included in this SAP. Impact of this variable is addressed in the subgroup analyses.

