## **4.4. Randomization**

Upon meeting all inclusion/exclusion criteria at baseline visit, subjects will be randomly assigned through IWRS in a 1:1 ratio to either of the treatment groups. The randomization will be stratified by region (North America, Europe, and Rest of World) and history of MAC lung infection (initial or subsequent). Subjects, Investigators, and the Sponsor will be blinded to treatment group assignments and microbiology results throughout the study. In case of subject emergencies, unblinding of the assigned treatment will occur per established procedure.

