#### **9.3.2.2. Analysis**

The analysis of change from baseline to Month 7 in respiratory symptom score (as assessed by QOL-B) will be summarized based on subjects in the ITT analysis set by treatment group.

The analysis model is the ANCOVA, the model includes response variable, ie, change from baseline to Month 7 and the following independent variables:

- history of MAC lung infection, (initial or subsequent)

- baseline QOL-B Respiratory domain score

The regression coefficient for treatment group in the ANCOVA is equal to the estimated population-level average treatment effect of  $\mu_{\text{ALIS}} - \mu_{\text{ELC}}$ ; this estimate will be used in Wald tests deriving p-value for the difference between the treatment groups. The p-value is nominal as the study is not a hypothesis testing and further is not powered for this comparison.

The summaries will include:

1. LS-mean of change from baseline to Month 7, differences of LS-mean changes from baseline (ALIS + background regimen minus ELC + background regimen) estimates and corresponding 95% CIs derived from ANCOVA model.
2. Descriptive statistics by timepoint with corresponding change from baseline.

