### 9.3.8. Subgroup Analysis

Treatment effect across major subgroups on the QOL-B Respiratory Symptoms Month 7, PROMIS Fatigue Month 7, and Conversion by Month 6 will be summarized. Subgroup factors are shown in the list below:

- Age: < 65 years, ≥ 65 years
- Gender: Female, Male
- Race: American Indian or Alaska Native, Asian, Black or African American, Native Hawaiian or Other Pacific Islander, White (races with small counts may be excluded from summaries)
- Stratification variable 'History of MAC lung infection': initial, subsequent
- Stratification variable 'Region': North America, Europe, and Rest of World
- MAC infection at baseline: Mycobacteria isolate species (*Mycobacterium avium* complex overall, *M. avium*, *M. intracellulare*), and other speciated and unspciated MAC)

The microbiological assessment analysis (MIC and susceptibility) will be summarized for the following subgroups:

- Stratification variable 'Region': North America, Europe, and Rest of World
- MAC infection at baseline: Mycobacteria isolate species (*Mycobacterium avium* complex overall, *M. avium*, *M. intracellulare*), and other speciated and unspciated MAC)

Subgroup analysis will use the same analytical approach as in the secondary endpoint analyses. Statistical modeling will not include history of MAC lung infection as covariate. Plots will not be generated for subgroups.

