## 10.5. Subgroup Analysis

Subgroup analyses will be performed on the following:

1. QOL-B non-respiratory symptoms Month 7
2. Subjects meeting WSMC QOL-B Month 7
3. Subjects meeting WSMC PROMIS Fatigue Month 7

Subgroup factors are shown in the list below:

- Age: < 65 years,  $\geq$  65 years
- Gender: Female, Male
- Race: American Indian or Alaska Native, Asian, Black or African American, Native Hawaiian or Other Pacific Islander, White (races with small counts might be excluded from summaries)
- Stratification variable 'History of MAC lung infection': initial, subsequent
- Stratification variable 'Region': North America, Europe, and Rest of World
- MAC infection at baseline: Mycobacteria isolate species (*Mycobacterium avium* complex overall, *M. avium*, *M. intracellulare*), and other speciated and unspciated MAC)

Subgroup analysis will use the same analytical approach as the main analysis. Statistical modeling will not include history of MAC lung infection as covariate.

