#### 11.1.5. Analysis of PRO Scores

PRO scores will summarize available data. Summaries will be presented by treatment group and by timepoint, as follows. Summaries will include:

1. Basic statistics of actual values and change from baseline to all protocol-specified timepoints.
2. LS-mean of change from baseline to Month 7, differences of LS-mean changes from baseline (ALIS + background regimen – ELC + background regimen) estimates and corresponding 95% CIs derived from ANCOVA model. The ANCOVA model will include change from baseline as response variable and treatment, baseline value, and history of MAC lung infection (initial or subsequent) as independent variables.

The following PRO scores will be summarized:

EXACT (see Section 11.1.1)

- EXACT Total score
- Breathlessness domain score
- Cough & Sputum domain score
- Chest Symptoms domain score

EXACT-RS (see Section 11.1.2)

- RS-Total score
- RS-Breathlessness subscale score

- RS-Cough & Sputum subscale score
- RS-Chest Symptoms subscale score

SGRQ (see [Section 11.1.3](#))

- Total score
- Symptom component score
- Activity component score
- Impact component score

FACIT – Fatigue Scale (see [Section 11.1.4](#))

- Fatigue subscale score

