#### 11.2.2.1. Analysis of PGI-S Scores

Change from baseline to Month 7 in PGI-S scores will be analyzed similarly to QOL-B respiratory domain, see [Section 9.3.2.2](#) for details.

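### Region, a randomisation stratum, is left out of the ANCOVAs for an empty-cell reason that does not apply to main-effects models, and 15 of the 23 scores have no regional subgroup analysis either

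*SAP*

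**What the plan says.** SAP 4.4 stratifies randomisation by region (three levels) and by history of MAC lung infection (two levels).

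SAP 9.1.2 multiplies these by two treatments to get 12 combinations. It notes that the trial has 100 subjects and states that "it is expected for some strata to have empty cells, resulting in inestimable parameters". On that ground it leaves region out of all models in the SAP while keeping history. It adds: "Impact of this variable is addressed in the subgroup analyses".

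The models concerned are these:

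- **9.3.2.2 (QOL-B respiratory):** "The analysis model is the ANCOVA, the model includes response variable, ie, change from baseline to Month 7 and the following independent variables" history and baseline score. The treatment term is missing from that list, but the next paragraph interprets its coefficient.
- **9.3.3.2 (PROMIS fatigue):** follows 9.3.2.2.
- **10.2.2 and 11.1.5:** "treatment, baseline value, and history of MAC lung infection (initial or subsequent) as independent variables".
- **11.2.2.1:** "Change from baseline to Month 7 in PGI-S scores will be analyzed similarly to QOL-B respiratory domain".

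None of these has an interaction term.

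Region appears as a subgroup factor in two places. In 9.3.8: "Treatment effect across major subgroups on the QOL-B Respiratory Symptoms Month 7, PROMIS Fatigue Month 7, and Conversion by Month 6 will be summarized", with MIC and susceptibility summaries also by region. In 10.5, where "Subgroup analyses will be performed on the following" introduces the QOL-B non-respiratory domains and the two meaningful-change responder analyses.

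Protocol 10.6.1 allows the ANCOVA and logistic models to omit the strata because of small counts. SAP 7.2 makes all these comparisons descriptive.

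**The concern.** An empty cell in the treatment-by-history-by-region table makes parameters inestimable when the model has a separate term for every cell. A main-effects model borrows across cells. It can estimate a region coefficient whenever that region has subjects and region is not an exact combination of the other terms. The reason in 9.1.2 therefore describes a model the SAP does not use.

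The substitute is also weak. A regional subgroup analysis shows whether the effect differs by region. It does not adjust the overall estimate for a factor that governed randomisation. It is also sparser than the model that was rejected, because it fits treatment and baseline score within one region's subjects. And it is planned for only some of the scores.

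What is at stake is the reported precision. Stratified randomisation balances the arms within region, so region contributes little to the true sampling variability of the treatment difference. An ANCOVA without region still counts between-region variation as residual error. If region is prognostic, the model-based standard errors and confidence intervals are then too wide.

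**Working it through.** **1. The plan's own figure.** 2 treatments × 2 histories × 3 regions = 12 cells, and 100 / 12 = 8.3 subjects per cell on average. The 12 is right, and empty cells are plausible.

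**2. Parameters.**

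| Model | Terms | Parameters | Residual df at N = 100 |
|---|---|---|---|
| Planned ANCOVA | intercept, treatment, history, baseline | 4 | 96 |
| With region as main effect | + 2 region terms | 6 | 94 |
| Fully crossed | 12 cell means + baseline | 13 | 87 |

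Adding region moves the two-sided 5% critical t from 1.9850 to 1.9855 (+0.03%).

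Worked example: regions of 60, 30 and 10 subjects, with 18, 6 and 0 subsequent infections, and arms alternating. Two of the 12 cells are empty. The main-effects design matrix has rank 6 of 6, so everything is estimable. The crossed model has rank 11 of 13. Only the crossed model fails.

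**3. How often would region be lost?** The documents give neither the regional split nor the share of subsequent infections, so both are assumed. Trials of 100 were simulated with permuted blocks of 4 within region × history.

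| Assumed settings | At least one of 12 cells empty | Region coefficient lost |
|---|---|---|
| Splits 40:30:30, 60:30:10, 75:20:5; subsequent 10% or 20%; 8,000 trials per setting | 6% to 97% | 0% at the first two splits; 0.5% to 0.7% at 75:20:5 |
| Splits from equal thirds to 70:25:5; subsequent 10% to 50%; 4,000 trials per setting | 0% to 96% | 0% to 0.6% |

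Exact check for a region with a 5% share: the chance that it gets no subjects is 0.95^100 = 0.6%.

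**4. Effect on precision.** Let R² be the share of variance left after baseline score and history that region explains (assumed). The reported SE with region, divided by the SE without, should be about √(1 − R²).

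| R² | √(1 − R²) | Simulated ratio of mean reported SE | CI width without / with region |
|---|---|---|---|
| 0 | 1 | 1.001 to 1.002 | 0.9997 |
| 5% | 0.975 | 0.975 to 0.976 | 1.026 |
| 10% | 0.949 | 0.949 to 0.950 | 1.054 |

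The last column is 1/√(1 − R²) × 1.9850/1.9855. The true sampling SD of the treatment estimate changed by at most 0.6% (ratio 0.994 to 1.002). Adding region therefore corrects the reported precision and hardly changes the estimator.

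**5. Subgroup coverage.**

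| Scores with a planned ANCOVA | SAP section | Number | Regional subgroup analysis |
|---|---|---|---|
| QOL-B respiratory | 9.3.2 | 1 | yes (9.3.8) |
| PROMIS fatigue | 9.3.3 | 1 | yes (9.3.8) |
| QOL-B non-respiratory domains | 10.2 | 6 | yes (10.5) |
| EXACT | 11.1.5 | 4 | none |
| EXACT-RS | 11.1.5 | 4 | none |
| SGRQ | 11.1.5 | 4 | none |
| FACIT-Fatigue | 11.1.5 | 1 | none |
| PGI-S respiratory and fatigue | 11.2.2.1 | 2 | none |

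Total 1 + 1 + 6 + 4 + 4 + 4 + 1 + 2 = 23. Covered: 1 + 1 + 6 = 8. Not covered: 23 − 8 = 15. If the two PGI-S scores are not counted, it is 13 of 21.

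**6. Can region also enter the imputation?** The completer-based MAR imputation of the PRO scores (Appendix I) draws on completers in the same arm. Assume 35 to 40 completers per arm. The chance that some region has no completer in at least one arm is about 0% at 40:30:30, 3% to 5% at 60:30:10, and 24% to 31% at 75:20:5. For the last split, the 5% region alone gives 1 − (1 − 0.95^40)² = 24% and 1 − (1 − 0.95^35)² = 31%. Region can enter when the split is moderate, but not always when one region is very small.

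**The case against.** The strongest case against has four parts.

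*The omission is allowed and the consequence is small.* Protocol 10.6.1 permits leaving out the strata, and the SAP drops less than it could because it keeps history. There is no bias, and true variability is almost unchanged. Any error makes intervals slightly too wide, which is the conservative direction. Nothing in the documents shows that region is prognostic. SAP 7.2 disclaims inference, 9.3.2.2 says the study is not powered for this comparison, and the primary objective is psychometric. All of this stands, and it limits the weight of the point. It does not make the estimability argument correct, and permission to omit is not a reason to omit.

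*The count of 15 flatters the gap.* All 15 scores are in SAP Section 11, and none is a listed secondary or exploratory endpoint. All 8 ANCOVA scores that are listed have a regional subgroup analysis. Some EXACT and EXACT-RS scores share the same items. This is fair. But the exclusion in 9.1.2 covers all analyses in the SAP, and its closing sentence carries no limit, so for those 15 scores it is not true as written. The case for adding region does not depend on the count.

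*One covariate set throughout is simpler.* In the logistic and Cox models a small region could have all or no converters. Sparse data is a sound reason to leave region out there, and no claim is made about those estimates.

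*Adding region unsettles the match with the imputation models.* At present the ANCOVA and the PRO imputation use the same baseline covariates. Region could not sensibly enter the retriever-based imputation or the ELC fallback, so some values would be imputed without it. This mismatch is real but minor, because the treatment contrast is balanced by region by design.

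**Conclusion.** The concern holds. The reason given in SAP 9.1.2 does not apply to the main-effects ANCOVAs. Under the assumed splits a region coefficient would be lost in fewer than 1% of trials, however often one of the 12 cells is empty. The statement that subgroup analyses address region is untrue for 15 of 23 scores, although it is true for all 8 that are listed secondary or exploratory endpoints.

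The effect is modest. If region is not prognostic, the reported SE barely moves. If it explains 5% or 10% of the remaining variance, intervals are about 3% or 5% wider than they should be. These sizes rest on assumed regional splits, infection-history shares, block size and R², none of which the documents give. There is no protocol deviation, no bias in the treatment estimate and no effect on the primary objective. The change is worth making because it costs almost nothing and brings the analysis into line with the randomisation.

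**What to change.** 1. Add region as a main effect, without interactions, to the ANCOVAs in SAP 9.3.2.2, 9.3.3.2, 10.2.2, 11.1.5 and 11.2.2.1. Name treatment explicitly in the 9.3.2.2 covariate list at the same time.
2. State a rule for combining regions, applied at the blinded data review, only if a region has no or almost no subjects. Write the minimum count into the SAP.
3. Include region in the completer-based MAR imputation of the PRO scores (Appendix I) where completer numbers per region and arm allow, with the minimum stated in advance. Keep the retriever-based and ELC-reference imputations and the conversion imputation as planned.
4. Rewrite the reason in 9.1.2. Region may stay out of the standardised logistic regression, the Cox model, the Cochran-Mantel-Haenszel test, the subgroup models and the small or binary imputation models, but because data within a region are sparse, not because cells are empty.
5. Replace the closing sentence of 9.1.2 with a statement of which endpoints have a regional subgroup analysis and which do not.

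The cost is two degrees of freedom per ANCOVA (96 to 94 at N = 100) and SAP wording. No new data are needed.

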### **9.2. Primary Endpoint**

There is not a single primary endpoint of this study given the objectives of this study. As per Section 3.1 there is a set of psychometric variables that are used to demonstrate the domain specification (via modern psychometric methods), reliability, validity, and responsiveness (within-subject meaningful change) of the PRO instruments. Detailed analysis plan is included in the VAP for the psychometric methods. VAP analysis results will be reported in a separate report (Validation Report).

### **9.3. Secondary Endpoints**

#### **9.3.1. Culture Conversion by Month 6**

##### **9.3.1.1. Variable Description**

###### MAC Culture Assessment

Microbiological assessment of sputum specimens is the secondary efficacy measurements in this study.

During the study, subjects are required to provide expectorated or induced sputum samples before dosing with the study drugs. To improve the chance of obtaining an acceptable sputum specimen for culturing, 2 sputum samples will be obtained from each subject at each assessment; subjects will provide 1 sputum sample on the day prior to the scheduled visit, and 1 sputum sample on the day of the visit, both are prior to dosing with study drugs. At Screening, subjects will provide 1 sputum sample on the day of the visit and 1 sputum during the week following the Screening visit. Both sputum samples from each visit will be assayed.

Sputum specimens will be cultured in broth media (liquid) in addition to agar media (solid) and will be held for up to 6 weeks. A negative culture result will not be reported

until after this time has transpired. All samples contaminated by organisms other than MAC will be re-processed and re-cultured once.

#### MAC culture negative

MAC culture negative is defined as no MAC growth on agar media and broth media in all sputum cultures at a visit. If at least one medium has a negative result, and no medium has a positive result, the MAC culture is negative. If all samples are contaminated, the MAC culture is considered negative. In case of contradictory culture results, ie, one sample positive and the other negative, the visit will be considered to have a positive culture for the purpose of analysis.

Single broth positive timepoints should be considered negative for MAC if preceded by conversion. This must be a single instance of positive broth. Single broth positive timepoints should be considered positive for MAC if preceded by non-conversion. The definition of recurrence supersedes this rule (e.g. if broth positive followed by positive broth consecutively at the next visit, then that meets definition of recurrence),

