8. EFFICACY ASSESSMENTS

8.1. Sputum Culture

Microbiological assessment of sputum specimens will be used for secondary efficacy measurements.

During the study, pre-dose expectorated or induced sputum samples (approximately 2 mL) are required at study visits specified in the Schedule of Assessments (Table 4). To improve the probability of obtaining a good sputum specimen, 2 sputum samples will be obtained from each subject at each assessment; subjects will provide 1 sputum sample on the day prior to the scheduled visit, and 1 sputum sample on the day of the visit prior to dosing with study drugs. At Screening, subjects will provide 1 sputum sample on the day of the visit and 1 sputum during the week following the Screening visit. If a subject is unable to produce sputum spontaneously, sputum may be induced. If after induction, a subject is still unable to produce sputum despite reasonable efforts, this will be recorded as non-productive at that time point. It is recommended to schedule an in-clinic visit as a backup to non in-clinic visits in case the subject is not able to spontaneously produce sputum at home. If a subject is unable to spontaneously produce sputum at home on the day prior to the scheduled visit, the subject should then come into the clinic for sputum induction on the scheduled visit. The induction should be performed within the specified visit window (Table 4). At the scheduled visit, once sputum is collected (spontaneously or by induction), study drugs can be administered. If the subject produces their best sputum samples first thing in the morning prior to being able to attend a clinic visit, the subject should consistently collect sputum samples first, then proceed with PRO assessments and other assessments throughout the study.

Sterile, leak proof, non-wax, disposable plastic containers labeled with 2 subject identifiers will be used to collect specimens aseptically to avoid contamination. Sputum samples should be refrigerated, not frozen, until shipped to the central microbiology laboratory as soon as possible to avoid overgrowth by contaminating normal flora. No fixative or preservatives are to be used with sputum samples. Detailed instructions for collecting, processing, and shipping sputum specimens will be provided in the site laboratory manual. Subjects will be provided with instructions for collecting, processing, and shipping sputum specimens for samples collected at non in-clinic visits.

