Sites are strongly discouraged from performing local mycobacterium sputum cultures for the duration of the study, as this may introduce bias to subject assessments. Sputum may be sent to local laboratories to be cultured for organisms other than mycobacterium.

Microbiological Assessment

Sputum specimens will be cultured in broth media (liquid) in addition to agar media (solid), and will be held for up to 6 weeks. A negative culture result will not be reported until after this time has transpired. All contaminated samples will be retreated and re-cultured once.

Growth of other bacteria due to co-infections (eg, *Pseudomonas aeruginosa*, *M. abscessus*, other NTM) will be reported as applicable. Colony counts of MAC growth will be reported. Isolates of MAC will be identified using a commercial RNA probe (AccuProbe, Gen Probe, Inc., GenoType NTM-DR Ver 1.0, Hain Lifescience) and subsequently identified to species using molecular

methodology (Cousins et al., 1996). Standard antibiotic sensitivity testing using MICs will be routinely performed on mycobacterial isolates (CLSI, 2018a; CLSI, 2018b; Forbes et al., 2008).

The MAC species and genotype at the Screening and/or Baseline sputum specimen will be identified by whole genome sequencing (Illumina Nextseq500TM) in subjects who achieve sputum culture conversion and who subsequently have positive sputum culture(s) (broth or agar); typing by whole genome sequencing will also be conducted.

MAC Culture Assessment Definitions

MAC culture negative	No MAC growth on agar media and broth media in all sputum cultures at a visit.
Non-productive	Prior to culture conversion or post recurrence: visits where subjects were recorded as non-productive are considered MAC culture positive. Post culture conversion: visits where subjects were recorded as non-productive are considered MAC culture negative.
Culture conversion	No MAC growth on agar media and broth media in all sputum cultures at 2 consecutive visits. The date of conversion is defined by the date of the first of 2 consecutive negative cultures.
Recurrence: Relapse	Subsequent to culture conversion, at least 1 MAC positive culture in agar media or positive cultures in broth media in at least 2 consecutive visits. A MAC positive culture is defined as the same species and genome as cultured at Screening/Baseline.

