#### Culture Conversion

Culture conversion is defined as MAC culture negative at 2 consecutive visits during the treatment period. The conversion status will be reversed by a positive culture after conversion (recurrence). As such, a subject may achieve culture conversion multiple times during the study. The date of conversion is defined by the date of the first of 2 consecutive negative cultures.

The secondary endpoint culture conversion by Month 6 is defined as MAC culture negative at Month 5 and Month 6 with the adjustment for non-productive sputum (described below) and additional rules described in [Section 9.3.1.2.1](#).

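### A visit at which every sputum sample is contaminated is scored MAC negative, so an unknown result can count as a first negative culture or as half of a conversion

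*SAP*

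**What the plan says.** SAP 9.3.1.1 first sets a minimum for a negative visit: "If at least one medium has a negative result, and no medium has a positive result, the MAC culture is negative". The next sentence covers a different case: "If all samples are contaminated, the MAC culture is considered negative". It applies whatever the subject's earlier culture status.

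On laboratory handling, the SAP says "All samples contaminated by organisms other than MAC will be re-processed and re-cultured once", and Protocol 8.1 says "All contaminated samples will be retreated and re-cultured once". The protocol's definition of a negative visit is "No MAC growth on agar media and broth media in all sputum cultures at a visit". Its table of definitions also covers non-productive visits, conversion and recurrence, but not visits that stay contaminated after re-culture. Protocol 8.1 presents contamination as a handling risk: samples are to be shipped "as soon as possible to avoid overgrowth by contaminating normal flora".

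The endpoints that use visit status are:
- time to first negative culture (SAP 9.3.5.1), where one negative visit is the event and Months 1 to 7 are presented;
- culture conversion and time to conversion (SAP 9.3.1.1 and 9.3.4.1), which need two consecutive negative visits;
- conversion by Month 6, where "The secondary endpoint culture conversion by Month 6 is defined as MAC culture negative at Month 5 and Month 6".

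**The concern.** A fully contaminated visit says nothing about whether MAC is present, yet it is recorded as a favourable result. The SAP justifies other handling choices, such as rule 4 and the imputation after intercurrent events in 9.3.1.2.1, but not this one. The rule is also less cautious than the one for non-productive visits, which SAP 9.3.1.1 scores as positive before conversion and after recurrence.

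The error can spread. A contaminated visit counts as observed, so it bypasses the missing-data rules in 9.3.1.2.1. After a false conversion, later non-productive visits become negative. The same holds for isolated broth positives: "Single broth positive timepoints should be considered negative for MAC if preceded by conversion". The subject also enters the recurrence denominator (SAP 9.3.7.2).

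Most exposed is time to first negative culture in subjects who rarely or never have a true negative. Conversion by Month 6 and time to conversion are affected less. Protocol 10.5.2 also uses converter status as an anchor for meaningful change, but no effect there can be shown without the Validation Analysis Plan.

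**Working it through.** The plan states no figure that depends on this rule, so there is none to reproduce. The figures below are illustrative.

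**Inputs**
- q = share of visits with all samples still contaminated: 1%, 3%, 5% (assumed)
- r = chance that a visit is truly negative: 0, 0.1, 0.3 (assumed)
- p = conversion rate at which unresolved statuses are imputed: 60% (assumed; Protocol 10.1 plans for 50% to 70% conversion)
- seven visits for first negative culture (SAP 9.3.5.1); Months 5 and 6 for conversion (SAP 9.3.1.1)
- visits independent (assumed)

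The fix makes a fully contaminated visit missing.

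**1. First negative culture within seven visits**

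- Current rule: 1 − [(1−r)(1−q)]^7
- Fix: 1 − [1 − r(1−q)]^7
- No contamination: 1 − (1−r)^7

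At q = 5%:
- r = 0: rule 1 − 0.95^7 = 0.302; fix 0.
- r = 0.1: rule 1 − 0.855^7 = 0.666; fix 1 − 0.905^7 = 0.503; difference 0.163.
- r = 0.3: rule 1 − 0.665^7 = 0.942; fix 1 − 0.715^7 = 0.904; difference 0.038.

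| r | Rule minus fix, in points, at q = 1% / 3% / 5% |
|---|---|
| 0 | 6.8 / 19.2 / 30.2 |
| 0.1 | 3.6 / 10.3 / 16.3 |
| 0.3 | 0.8 / 2.4 / 3.8 |

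At r = 0.3 the chance without contamination is already 1 − 0.7^7 = 91.8%, and the current rule adds only 0.6, 1.6 or 2.5 points to it.

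**2. Conversion by Month 6 (r = 0.3, p = 0.6, rule 4 of SAP 9.3.1.2.1 ignored)**

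- Current rule: [r(1−q) + q]²
- Fix, with any observed positive a non-converter: [r(1−q)]² + p[2r(1−q)q + q²]
- Difference: (1−p)[2r(1−q)q + q²]

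At q = 5%: rule 0.335² = 0.1122; fix 0.285² + 0.6 × 0.031 = 0.0998; difference 0.4 × 0.031 = 0.0124.

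| | q = 1% | q = 3% | q = 5% |
|---|---|---|---|
| Current rule | 9.4% | 10.3% | 11.2% |
| Fix | 9.2% | 9.6% | 10.0% |
| Difference, points | 0.2 | 0.7 | 1.2 |

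At q = 5% the difference is 1.6 points with p = 0.5 and 0.9 with p = 0.7. If 20 subjects in an arm of 50 are of this kind, the arm proportion moves by 20/50 of the difference: 0.1, 0.3 or 0.5 points.

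**3. Why the fix needs a second sentence**

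The definition in SAP 9.3.1.1 implies that a positive at Month 5 or Month 6 makes a non-converter. But the justification of rule 4 says status is undetermined when one of the two visits is missing, and 9.3.1.2.1 has no explicit non-converter line like the one in SAP 11.3. Read literally, a subject with one positive and one contaminated visit would be imputed. That adds p × 2(1−r)(1−q)q = 0.0083, 0.0244 or 0.0399. At q = 5%: 0.0998 + 0.0399 − 0.1122 = 0.0275. Conversion would then be 0.6, 1.7 or 2.8 points higher than under the current rule, not lower.

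A simulation of 2,000,000 subjects at q = 5%, r = 0.3, p = 0.6 gave 0.1121 (rule), 0.0997 (fix) and 0.1398 (fix without the second sentence), in agreement with the formulas.

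**The case against.** **The rule only adds detail.** Read literally, a plate overgrown by other organisms shows no MAC growth, and SAP section 2 lets the SAP add detail and prevail over the protocol. This stands in part: the absence of the rule from SAP Table 9 is weak evidence of an undeclared change. But the protocol does not say that an unreadable culture is negative, and SAP 9.3.1.1 itself treats contamination separately from a negative result.

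**The rates are assumed and the safeguards are real.** There are two samples per visit, two media and one re-culture, and the rule applies only when everything fails. This stands. The large figures belong to subjects with no or few true negatives, and no arm-level figure is available for time to first negative culture.

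**For likely converters the fix may merely reverse the error.** With the Month 6 formulas above, rule 4 ignored, and an assumed mix of 60% of subjects at r = 0.9 and 40% at r = 0.3, the current rule errs by +0.3, +0.8 and +1.4 points against no contamination, and the fix by −0.3, −0.7 and −1.2. This does not survive once rule 4 is applied, because it keeps many earlier converters with one missing visit. In a simulated population with about 56% conversion and rule 4 applied, the current rule erred by +0.2, +0.6 and +1.0 points and the fix by about 0.0, 0.0 and −0.1.

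**The stakes are low.** The endpoints are secondary, SAP 7.2 disclaims inference, the rule is the same in both arms, and microbiology is blinded. This limits the severity but does not justify the rule.

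**Conclusion.** The concern holds. The SAP records an unknown result as a favourable one, without a reason, and treats it more leniently than a non-productive visit. The effect on time to first negative culture can be material for persistently positive subjects: 6.8 to 30.2 points if none of their visits is truly negative and 1% to 5% of visits are fully contaminated. It is small for subjects often negative, and for conversion by Month 6 (0.2 to 1.2 points per affected subject type, 0.1 to 0.5 points per arm in the example). All sizes rest on assumed contamination rates and independent visits. An effect on the primary validation is not shown. The rule should be changed, but the secondary, descriptive status of these endpoints keeps the point below critical.

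**What to change.** Make two changes together.

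1. In SAP 9.3.1.1, replace the contamination sentence with: *If all samples at a visit remain contaminated after re-culture, the visit is missing and cannot count as a negative culture.*
2. In SAP 9.3.1.2.1, before rule 5, add: *A subject whose Month 5 or Month 6 culture is positive, after the non-productive and single-broth-positive rules of 9.3.1.1, is a non-converter by Month 6 whether or not the other culture is missing.*

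Add a sensitivity analysis that scores fully contaminated visits as positive, and report their number by arm.

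The cost is two sentences, a small derivation change, one table and one count. A few visits become missing. A contaminated visit between two negatives would break the pair and could delay the conversion date. A subject contaminated at both Month 5 and Month 6 would be imputed instead of being called a converter. Rule 4 still protects earlier converters with one missing visit who meet its criteria.
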